## 9. STATISTICAL DESIGN

A Statistical Analysis Plan (SAP) will be written and finalized prior to database lock. The following is a brief description of the analyses to be described in this plan. The SAP will be more detailed and account for all analyses. All analyses will be conducted with statistical software SAS Version 9.4 or later.

### 9.1 GENERAL

The subject data will be described and summarised using the baseline demographic and medical variables, which include, but are not limited to, age, gender, ethnicity, medical and medication history, diagnostic factors as well as study process variables (e.g. AE and withdrawal(s)). Summary statistics will be given according to the nature of the variable, continuous or categorical. For continuous variables, the number of observations, mean, standard deviation, median, minimum, and maximum will be presented, while for categorical variables the number of observations, frequency, and percentages will be reported.

Primary, secondary, and exploratory outcome variables and derived variables will also be summarised accordingly. Parametric statistical tests will be used if the data are normally distributed and corresponding non-parametric tests will be considered if the data are not. Where necessary, suitable regression techniques will be used to adjust for confounding variables since the study is non-randomised. The results will be reported at 5% significance level and where appropriate 95% confidence intervals will be given.

## 9.2 ANALYSIS POPULATIONS

- Intention to Treat population (ITT), including all subjects randomized into the study.
- Full analysis set population (FAS), following Intention to Treat principle including all subjects who were randomized into the study and attended at least one post-baseline assessment
- Safety Population (SAF), including all subjects who have received the IP or the control devices.
- Per-Protocol Population (PP), including all subjects in the full analysis set who have no significant protocol deviations and met the inclusion/exclusion criteria.

Statistical analysis will be performed using each of the patient populations as follows. Analysis of the primary, secondary and exploratory efficacy objectives will be performed separately using both the Full Analysis Set and the Per Protocol Population. All safety analyses will utilize the Safety Population.

## 9.3 BASELINE DATA

The subjects will be described and summarised using the baseline demographic and medical variables, which include, but are not limited to, age, gender, ethnicity, medical and medication history, diagnostic factors. Summary statistics will be given according to the nature of the variable, continuous or categorical. For continuous variables, the number of observations, mean, standard deviation, median, minimum, and maximum will be presented, while for categorical variables the number of observations, frequency, and percentages will be reported. A complete accountability report, along with the explanation for lost-to-follow-up, death, revision, and withdrawn subjects will be provided with the methods being detailed in the SAP.

## 9.4 EFFICACY ANALYSIS

The study is non-comparative and non-randomized, single cohort, post-marketing, multicenter prospective study to evaluate the clinical outcomes of the CONQUEST FN™ Femoral Neck Fracture System. A minimum total of 90 subjects will be enrolled in the study, which includes a 5% estimate for subjects lost to follow-up at 1 year.

#### 9.4.1 Analysis of Primary Endpoint

A two-sided confidence interval will be provided for the proportion of re-operation (i.e. re-operation rate) for any reason of displaced and non-displaced femoral neck fractures treated with CONQUEST FN™ at one-year post-operation.

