### **8.3 STUDY ENDPOINTS**

#### **8.3.1 Primary Endpoint**

The primary endpoint of this study is the re-operation rate for any reason of displaced and non-displaced femoral neck fractures treated with CONQUEST FN™ at one year post-operation.

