#### **8.4.5 Exit Visit: 12 months (Day 365 $\pm$ 30 days)**

1. Assess level of pain from the target hip within the previous 24 hours using the VAS.
2. Instruct the subject to complete the health outcome questionnaire, EQ-5D-5L.
3. Complete ASLR test as instructed in Section 8.5, Study Methods and Measurements.
4. Complete TUG test as instructed in Section 8.5, Study Methods and Measurements.
5. Query subject regarding any changes in general health, the use of concomitant medications, and ambulatory status
6. If any adverse device effects or device deficiencies are observed or reported, they must be recorded as instructed in Section 11, adverse events and device deficiencies.
7. Perform radiology imaging collecting both AP and lateral images of the target hip.
8. Complete Exit Visit CRF

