## **10. SAMPLE SIZE JUSTIFICATION**

Precision Analysis was used to assess the overall proportion of re-operation rate for any reason of displaced and non-displaced femoral neck fractures treated with the CONQUEST FN™ Femoral Neck Fracture System at one-year post-operation. Assuming a 5% lost to follow-up rate after the first year, a minimum of 90 subjects will be enrolled (based on the inclusion/exclusion criteria) in order to complete 80 evaluable subjects. The 90 subjects will be enrolled to allow a minimum of 45 subjects with each of the following indications to be recruited: displaced or non-displaced femoral neck fractures. For the displaced group this number of subjects is sufficient to estimate the proportion of success rate to within 12% by use of the two-sided 95% confidence interval (assuming an overall success rate of 87%). And for the non-displaced group this number of subjects is sufficient to estimate the proportion of success rate to within 10% use of the two-sided 95% confidence interval (assuming an overall success rate of 93%).

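### The primary re-operation rate is planned as a crude one-year proportion, with no stated handling of subjects lost before one year

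*Combined protocol and SAP*

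**What the plan says.** - Section 8.3.1 sets the endpoint: "The primary endpoint of this study is the re-operation rate for any reason", at one year post-operation.
- Section 9.4.1 is the only text on its analysis: "A two-sided confidence interval will be provided for the proportion of re-operation (i.e. re-operation rate) for any reason". No estimator, denominator or missing-status rule follows. Section 9.1 adds the confidence level: "The results will be reported at 5% significance level and where appropriate 95% confidence intervals will be given".
- Section 9.2 runs efficacy on both the full analysis set (FAS) and the per-protocol set, without saying which is primary. FAS membership needs only that the subject "attended at least one post-baseline assessment"; one-year status is not required.
- Section 10 enrols 90 "in order to complete 80 evaluable subjects", with 5% loss to follow-up. Its precision targets are 12 points for displaced fractures (assumed success 87%) and 10 points for non-displaced fractures (93%).
- Section 9.3 promises a listing: "A complete accountability report, along with the explanation for lost-to-follow-up, death, revision, and withdrawn subjects will be provided", with methods left to the SAP. This accounts for subjects but does not say how they enter the rate.
- Section 9 describes itself as brief and defers to a SAP to be finalised before database lock. The supplied documents contain no separate SAP text.

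**The concern.** A subject who leaves event-free at month 3 has been observed for a quarter of the risk period. A simple proportion can count that subject as a full-year non-event or leave the subject out. The first choice understates the one-year risk, because re-operations after the loss go unseen. The second overstates it, because subjects re-operated before leaving still count while event-free leavers do not. The plan's own wording points to the first choice in Section 9.2 and the second in Section 10.

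The reported primary rate would then depend partly on follow-up and on an unstated choice of denominator. This remains true even if every subject whose hardware is revised is kept in the analysis, so it is separate from the withdrawal rule in Section 7.7.1.

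**Working it through.** **Inputs.** Section 10: re-operation risk p = 1 − 0.87 = 13% (displaced) and 1 − 0.93 = 7% (non-displaced); 45 enrolled per type; 80 evaluable, so about 40 per type; stated loss 5%. Assumptions: loss and re-operation times are independent and even over the year, with no deaths in steps 2 to 4.

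**1. The plan's own figures.** 95% half-width = 1.96 × √(p(1−p)/n), plus 1/(2n) with continuity correction.
- Displaced, n = 40: 1.96 × √(0.1131/40) = 10.4 points; corrected 11.7.
- Non-displaced, n = 40: 1.96 × √(0.0651/40) = 7.9 points; corrected 9.2.
- At n = 45 the corrected values are 10.9 and 8.6.

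The targets of 12 and 10 points are reproduced as half-widths. The enrolment step is looser: 80/0.95 = 84.2, so 85 would do, and going from 90 to 80 is 10/90 = 11.1% loss.

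**2. Crude rate under each denominator.** With loss fraction L, half the events among lost subjects fall after they leave.
- Observed events per enrolled subject: p(1−L) + pL/2 = p(1 − L/2). This is the reading with everyone kept.
- Event-free leavers: L(1−p) + Lp/2. Dropping them gives p(1 − L/2) / [1 − L(1−p) − Lp/2].

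For p = 13%, L = 5%: 0.13 × 0.975 = 12.7%; and 0.12675/(1 − 0.0435 − 0.00325) = 0.12675/0.95325 = 13.3%.

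| True risk | Loss | All kept | Leavers dropped |
|---|---|---|---|
| 13% | 5% (stated) | 12.7% | 13.3% |
| 13% | 11.1% (90 to 80) | 12.3% | 13.7% |
| 13% | 20% (assumed) | 11.7% | 14.4% |
| 7% | 5% (stated) | 6.8% | 7.2% |
| 7% | 11.1% (90 to 80) | 6.6% | 7.4% |
| 7% | 20% (assumed) | 6.3% | 7.8% |

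A constant-hazard calculation gives the same rounded values at 5% and 11.1%.

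**3. Applying the FAS entry rule.** If the first post-baseline assessment is the week-6 visit, subjects lost before day 42 leave the FAS. With a = 42/365 = 0.115, the FAS rate is p[(1−L) + L(1−a²)/2] / (1 − La). For p = 13% this gives 0.12671/0.99425 = 12.7% at 5% loss, 0.12268/0.98722 = 12.4% at 11.1%, and 0.11683/0.97699 = 12.0% at 20%. The downward bias shrinks a little but stays.

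**4. Bounds for unknown status.** Take 45 enrolled and 40 with known status.
- Displaced, 5 events (0.13 × 40 = 5.2): 5/45 = 11.1% if no unknown subject was re-operated, and 10/45 = 22.2% if all were.
- Non-displaced, 3 events: 3/45 = 6.7% to 8/45 = 17.8%.

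**5. Deaths.** Assume 20% deaths plus 5% loss, with constant hazards h = −ln(0.87) = 0.1393 (re-operation), −ln(0.80) = 0.2231 (death) and −ln(0.95) = 0.0513 (loss).
- Cumulative incidence, death competing: (0.1393/0.3624) × (1 − 0.87 × 0.80) = 11.7%.
- All enrolled kept: (0.1393/0.4137) × (1 − 0.87 × 0.80 × 0.95) = 11.4%.
- Deaths and losses both dropped: 0.114/(0.114 + 0.661) = 14.7%.

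The gap of 0.3 points between the first two comes from the losses. Keeping deaths as non-events adds no bias to this quantity; dropping them moves it by 3 points.

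**The case against.** The strongest reply has four parts.

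**The shift is small.** At the only loss rate the protocol states, each denominator is about 0.3 points from the true rate, against planned precision of 10 to 12 points. This stands. Losses above 11% have no source in the documents.

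**The rule is unstated rather than wrong.** Section 9.4.1 fixes no denominator, and FAS membership does not itself say that unknown status counts as a non-event. This stands too: both readings are inferences. But neither denominator recovers the one-year risk when subjects are lost early, so naming one would not be enough.

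**The SAP may settle it.** It may, but that text is not supplied. Section 9 requires it only before database lock, and Section 9.6 plans an outcome summary once the last subject passes 6 months. The choice could therefore follow sight of the results.

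**Cumulative incidence does not cure missing status.** Correct. Censoring assumes non-informative loss, so the bounds in step 4 are still needed.

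A reader might also infer three stronger points that the documents do not support:
- *That deaths counted as non-events dilute the rate.* Under a competing-risk estimand they do not. Without censoring, the Aalen-Johansen estimate is events divided by subjects.
- *That the exit window ("Exit Visit: 12 months (Day 365" ± 30 days) makes the risk period vary.* The endpoint is set at one year. Using 1 − 0.87^(t/365), 13% becomes 12.0% at day 335 and 14.0% at day 395, but only if every subject exits at the same extreme. Exits spread evenly average 13.0%. The window matters only if re-operations are not cut at day 365.
- *That a comparison with published rates is biased.* Section 9.4 calls the study non-comparative, and no performance goal is set.

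**Conclusion.** The point holds as a cheap improvement to the primary analysis; it does not show that the planned result would be badly wrong. A crude proportion with no handling of early loss is biased down if lost subjects are kept and up if they are dropped, and the plan supports both readings. For a true 13%, the size is about 12.7% or 13.3% at 5% loss and about 12.3% or 13.7% at 11%, given non-informative loss spread evenly over the year. It becomes material if loss is higher or is related to outcome. The bounds of 11.1% to 22.2% for 5 events and 5 unknowns among 45 show how much then rests on an unstated rule. Death and the visit window need to be specified, but neither is shown to be a source of bias.

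**What to change.** In Section 9.4.1, and in the SAP:

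1. Estimate the re-operation rate as the cumulative incidence at day 365 from dated re-operations (Aalen-Johansen), with loss to follow-up censored and death as a competing event. Give a 95% confidence interval for each fracture type and overall.
2. Keep the crude proportion with an exact confidence interval as a supporting analysis, and state its denominator.
3. Add best-case and worst-case bounds for subjects of unknown one-year status.
4. Confirm that the CRF records dates of re-operation, death and last contact. Section 8.5 asks for assessment dates, and the section on discontinued subjects asks for a date when consent is withdrawn. No section lists a date of re-operation or death.

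The cost is wording, plus a CRF check; no subjects or visits are added. The downside is that the asymptotic interval is rough with few events per type (0.07 × 45 = 3.2 to 0.13 × 45 = 5.9, so about 3 to 6). That is why the exact interval stays alongside.

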#### 9.4.2 Analysis of Secondary Endpoint(s)

The rate or mean of the following outcomes at 1 year post-operation will be reported:

- Intraoperative complications
- Radiographic outcomes including quality of fracture reduction
- Construct failure past typical femoral neck fracture healing period (past 6 months)
- Visual analogue scale (VAS) relating to pain at the fracture site
- Quality of Life (EQ-5D-5L)
- Time to return to full weight-bearing
- Ambulatory status from pre-injury to study completion
- Timed Up & Go
- Length of hospital stay
- Hospital readmission for any reason
- Device and surgery related adverse events
- Active straight leg raise (ASLR) assessment

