## **8. STUDY DESIGN**

### **8.1 STUDY DESIGN**

This is a multi-center, post-marketing, prospective study. Subjects will be stratified by fracture type (minimum of 45 displaced and 45 non-displaced fractures) for a minimum total of 90 enrolled subjects.

Data from eligible subjects who have provided a signed ICF will be evaluated at the pre-operative, operative/discharge, 6-weeks, 3-month, 6-month and 12-month follow-up visits.

The total study duration will include approximately 18 months for enrollment and one year of follow-up at approximately 10 sites in the United States.

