#### CONFIDENTIAL AND PROPRIETARY

This document contains information that is confidential and proprietary to Smith & Nephew PLC and Smith & Nephew, Inc. and is intended for use only by Smith & Nephew and its manufacturer. It shall not be reproduced or copied in whole or in part, nor shall the contents be disclosed by any means without prior written permission from Smith & Nephew, nor shall anyone make any use of it that is contrary to the expressed or implied wishes of Smith & Nephew.

Study Protocol—Device	
A Multicenter, Post Market, Prospective Study Evaluating Safety and Efficacy of CONQUEST FN™ for the Treatment of Intracapsular Femoral Neck Fractures	Number: 18-3047-02 Version: 2.0, 30Nov2018 Page: Page 28 of 63

5. Query subject regarding any changes in general health, the use of concomitant medications, and ambulatory status
6. If any adverse device effects or device deficiencies are observed or reported, they must be recorded as instructed in Section 11, adverse events and device deficiencies.
7. Perform radiology imaging collecting both anteroposterior (AP) and lateral images of the target hip.
8. Instruct the subject on proper postoperative care documenting continued instructions in the subject's source document.
9. Instruct the subject on follow-up procedures, including returning to the office for FU Visit 2 in 90 ( $\pm$  7) days and Visit 3 in 180 ( $\pm$  14) days

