#### **8.4.7 Concomitant Medications and Therapies**

##### **CONFIDENTIAL AND PROPRIETARY**

This document contains information that is confidential and proprietary to Smith & Nephew PLC and Smith & Nephew, Inc. and is intended for use only by Smith & Nephew and its manufacturer. It shall not be reproduced or copied in whole or in part, nor shall the contents be disclosed by any means without prior written permission from Smith & Nephew, nor shall anyone make any use of it that is contrary to the expressed or implied wishes of Smith & Nephew.

Study Protocol—Device	
A Multicenter, Post Market, Prospective Study Evaluating Safety and Efficacy of CONQUEST FN™ for the Treatment of Intracapsular Femoral Neck Fractures	Number: 18-3047-02
	Version: 2.0, 30Nov2018
	Page: Page 29 of 63

A concomitant medication (e.g. drug, substance) and a concomitant therapy (e.g. physical therapy, TENS Unit, massage) are recorded pre-operatively and at each visit through the subject's last study visit. The subject's ambulatory status will be documented pre-operatively and at each follow-up through the last study visit.

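### Time to return to full weight-bearing: a mean or median of observed times, which the plan names, would describe achievers only, and the plan does not choose the rate that would include everyone

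*Combined protocol and SAP*

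**What the plan says.** Section 8.3.2 of the protocol names the endpoint, and Section 9.4.2 lists it again as "Time to return to full weight-bearing". Its only specific analysis is the lead-in shared by all twelve secondary outcomes: "The rate or mean of the following outcomes at 1 year post-operation will be reported". The list mixes counts, scores, durations and radiographic grades and does not match a summary to each item.

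Section 9.1 supplies the general rule: "For continuous variables, the number of observations, mean, standard deviation, median, minimum, and maximum will be presented". Section 9.2 sets the populations: "Analysis of the primary, secondary and exploratory efficacy objectives will be performed separately using both the Full Analysis Set and the Per Protocol Population". Neither population is limited to subjects who reach full weight-bearing, and neither assigns a time to those who do not.

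On data, Section 8.1 says subjects "will be evaluated at the pre-operative, operative/discharge, 6-weeks, 3-month, 6-month and 12-month follow-up visits". At follow-up, Section 8.4.4 has the site "Query subject regarding any changes in general health, the use of concomitant medications, and ambulatory status", and Section 8.4.7 says that "ambulatory status will be documented pre-operatively and at each follow-up through the last study visit". These steps do not list a date of full weight-bearing. The case report form is not among the documents.

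Section 9 describes itself as brief and promises of the later plan: "The SAP will be more detailed and account for all analyses".

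**The concern.** This is a time-to-event outcome. Some subjects may never have the event within 12 months, and others may stop being observed before it. Section 4.1 describes non-union, avascular necrosis and implant failure as typical complications. Section 7.7.1 allows withdrawal after hardware is revised or exchanged, and Section 7.7.3 stops data collection once consent is withdrawn.

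A subject without the event has no observed time. The summaries in Sections 9.4.2 and 9.1, taken at face value, can use only observed times. The resulting figure would describe how quickly those who recovered did so, and would carry no information on how many did not. It could be read as the recovery time of patients treated with the device, and it can look better if the slowest patients are the ones who never get there.

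**Working it through.** The plan gives no figure for this endpoint, so there is nothing to reproduce. The check has a textual part and an arithmetical part.

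**Text.** The current sections contain no time-to-event method, no censoring rule, no assigned value for a non-achiever, and no rule for death, revision, withdrawal or loss before full weight-bearing. Section 9.3 promises an accountability report on lost, deceased, revised and withdrawn subjects. That is a disposition report, not a rule for this endpoint.

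**Inputs.** Follow-up visits are at Days 42, 90, 180 and 365 (Section 8.4). The share q who never achieve and the achievers' mean m are not in the documents. I assume q from 5% to 30% and m from 60 to 120 days, with no other losses.

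**Median.** For untied times, half of the achievers have achieved by their own median. As a share of all subjects that is (1-q)/2. The median over all subjects is therefore the achievers' 0.5/(1-q) quantile. As a count: if 27 of 90 never achieve, 63 do, their median is the 32nd time, and 32/90 = 35.6% of all subjects.

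**Mean.** Counting non-achievers at 365 days, the mean over all subjects restricted to 365 days is (1-q)·m + q·365. The achievers' mean stays at m. The shortfall is q·(365-m).

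| q (assumed) | All subjects who have achieved by the achievers' median | Achievers' percentile at the all-subject median | Achievers' mean (assumed) | Restricted mean, all subjects |
|---|---|---|---|---|
| 5% | 47.5% | 52.6 | 90 days | 103.8 days |
| 10% | 45% | 55.6 | 90 days | 117.5 days |
| 20% | 40% | 62.5 | 90 days | 145.0 days |
| 30% | 35% | 71.4 | 90 days | 172.5 days |

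For example, at 30%: 0.70·90 + 0.30·365 = 172.5. Over m = 60 to 120 days, the shortfall runs from 0.05·(365-120) = 12 to 0.05·(365-60) = 15 days at q = 5%, and from 0.30·(365-120) = 74 to 0.30·(365-60) = 92 days at q = 30%.

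**Direction.** The table holds m fixed. As a further illustration, assume exponential times with an 84-day median, so the rate is r = ln2/84 and 1/r = 121.2 days. The mean of times observed by day T is 1/r - T·exp(-rT)/(1-exp(-rT)).

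- If never achieving is unrelated to speed, T = 365 and the achievers' mean is 102 days whatever q is. The all-subject median solves (1-q)(1-exp(-rt)) = 0.5, giving 84 days at q = 0 and 152 days at q = 30%.
- If the slowest 30% are the ones who never achieve, T = -ln(0.30)/r = 145.9 days and the achievers' mean falls from 102 to 59 days. The figure improves because fewer patients recover.

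**Ties.** If only visit days were recorded, the median might not move at all. With 80 subjects and achievers split 40/40/20 over Days 42, 90 and 180, the achievers' median and the all-subject median are both 90 days for q from 5% to 30%. The restricted mean still moves from 103.8 to 172.8 days, while the achievers' mean stays between 87 and 90.

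**The case against.** The strongest reply is that nothing obliges the sponsor to use observed times only. A reader might infer from the silence that any mean or median reported here must be achievers-only. The documents do not support that. The quoted line allows a rate, which would keep non-achievers in the denominator. A Kaplan-Meier median or a restricted mean is also a median or mean time, and covers all subjects. What stands is that the plan names none of these for this endpoint.

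Second, Section 9 expressly defers detail to a later SAP, and a censoring rule for one descriptive endpoint is ordinary SAP content. That is fair and lowers the severity. But the protocol already names a summary, and the one it names does not suit this outcome.

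Third, Section 9.1 prints the number of observations beside each mean, so 63 of 90 would be visible, and Section 9.3 accounts for losses. This helps, but an n of 63 does not separate subjects who never recovered from those who were lost.

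Fourth, every day count above rests on assumed inputs. That is correct: they show direction and range and do not estimate the bias. At q = 5% the median shift is small.

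A reader might also infer that no date of full weight-bearing is collected. The visit steps do not list one, but without the case report form its absence is not shown.

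**Conclusion.** The point holds as a conditional one. If the mean or median of observed times is used, as Sections 9.4.2 and 9.1 name, the summary covers achievers only and does not register the share who never recover. The exact statement for untied times is (1-q)/2, with q unknown. On the assumed ranges, the achievers' mean falls 12 to 92 days short of the 365-day restricted mean over all subjects. The documents do not show how the final analysis was or will be done, because the SAP may still add the rule.

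The severity is minor. The study is single-arm and non-comparative, no test or decision is tied to this endpoint, and ambulatory status, Timed Up & Go, active straight leg raise and re-operation would still show non-recovery.

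A reader might extend the point to the primary endpoint, on the view that withdrawal after revision removes re-operations. The documents do not support this. The circumstances of withdrawal go on the End of Study form, adverse events of any kind are recorded, and nothing excludes a re-operation that came before withdrawal.

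**What to change.** In Section 9.4.2 and the SAP, state which summary applies to this endpoint. Report the cumulative incidence of return to full weight-bearing over all FAS subjects, with losses censored at last contact and death as a competing event, and say how subjects revised beforehand are counted. If no event date is captured, report instead the percentage of all FAS subjects who have achieved it by the 6-week, 3-, 6- and 12-month visits. Give the all-subject median if it is reached. If a mean is kept, label it as achievers only and print n/N beside it. Check whether the case report form holds the date before choosing between the two.

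The cost is a few lines of SAP text and code, with no added visits or subjects. The reported figure may be less favourable than an achievers-only mean.
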